- The median of the response times for all trials in which the subject picked the correct choice on the first attempt.
- Response time variable in milliseconds (ms), a positive unbounded variable, with higher values indicating slower performance across correct trials.
- Data were modeled using a normal distribution (i.e., the standard linear model).

2.7. The stop signal reaction time from the Stop Signal Task (**SST**) module.

- The estimate of the duration at which a person can successfully inhibit a response 50% of the time, represents the time before which all actions become ballistic and a subject is unable to cancel a response selection.
- Response time variable in milliseconds (ms), ranging from 0 to 500 ms, with higher values indicating that it takes longer for a person to inhibit a response.
- Data were modeled using a normal distribution (i.e., the standard linear model).

2.8. The total number of between errors from the Spatial Working Memory (**SWM**) module.

- The number of times a subject incorrectly revisited a box that had contained a token in a previous trial across the 4, 6, and 8 box conditions.
- Count variable, ranging from 0 to 63, with higher scores indicating worse performance.
- Data were modeled using a binomial distribution using the log-odds link function.

2.9. The participant's strategy for the 6-8 box conditions from the **SWM** module.

- The number of times subjects began a new search from the same box they started on in previous trials. It is assumed that a person who begins from the same box each time is using a planned strategy to find the tokens.
- Count variable, ranging from 2 to 14, with higher scores indicating low strategy, meaning a subject began searches from many different boxes.

- Data were shifted to range from 0 to 12 and were modeled using a binomial distribution using the log-odds link function.

Statistical model

We analyzed all outcomes via regression models fit using generalized estimating equations (GEE; Liang & Zeger, 1986). Note the GEE approach provides robust estimates of coefficients even when distributional assumptions are violated and when heteroscedasticity is present. We assumed data were clustered over subjects, and that the observations for a subject per each study visit were uncorrelated (The GEE method is also robust to misspecification of the correlation structure for a subject's observations).

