Continuous outcomes (e.g., latencies and reaction times) were fit using a standard linear regression model. Bounded count outcomes (e.g., number of errors or correct responses) were fit using binomial regression. Specifically, let $y_{(p,t)}$ refer to the outcome value for participant p at time t , where $y_{(p,t)} = \{0, 1, \dots, H\}$ with H referring to the highest possible value. We assumed that $y_{(p,t)}$ was distributed according to a binomial process governed by a latent probability $\theta_{(p,t)}$:

$$y_{(p,t)} \sim \text{Binomial}(\theta_{(p,t)}).$$

The log-odds of this latent probability can then be decomposed into the weighted sum of the predictors of interest.

In contrast to linear regression, which includes a parameter for the residual standard deviation, binomial regression has no additional parameter to handle overdispersion. While failure to account for overdispersion can lead to underestimation of standard errors, as noted before the GEE approach is robust to misspecification of distributional assumptions and corrects for this underestimation, and as such we did not need to implement any additional steps to address overdispersion issues.

Key confirmatory effect

The key confirmatory effect of interest for each outcome will be a dummy-coded contrast between CB-Mon (the referent, coded as 0) and CB-Abst (coded as 1), testing whether a constant effect of abstinence exists, averaged over all time points.

Multiple comparisons

Each module/task from the CANTAB examines a separate cognitive process of interest. We therefore address multiple comparisons issues within each module. As the number of outcomes per module range from 1 to 4, we used a simple Bonferroni correction, dividing the desired error rate of 5% by the number of outcomes per module. Therefore, effects of interest were flagged as statistically significant for $\alpha = 0.05$ (for the SST module), $\alpha = 0.025$ (for the PAL, SSP, OTS, and SWM modules), $\alpha = 0.0167$ (for the VRM module), and $\alpha = 0.0125$ (for the MTT module).

Covariates

The covariates we included for the primary analysis were:

- A coefficient for a linear trend to capture change over time, coded as week 1 = -3, week 2 = -1, week 3 = 1, and week 4 = 3.
- A subject's baseline value for a given outcome, converted to a z-score.

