In other words, we assume a conservative additive model, adjusting for baseline levels and with main effects for a) the impact of abstinence and b) change over time, but no treatment by time interaction.

Additionally, to assess the robustness of our conclusions we will incorporate, at a minimum, the following covariates as part of a secondary analysis:

- Age of participant at baseline (in years).
- Biological sex (male versus female).

Baseline scores from the Cannabis Use Disorder Identification Test - Revised (CUDIT-R; Adamson et al., 2010). The CUDIT-R is an 8-item scale with scores ranging from 0 to 32, where higher scores indicate more problematic cannabis use (a score of 8 or higher indicates hazardous use, while a score at or above 12 indicates a possible use disorder).

Missing data

Missing outcome data (e.g., subjects who did not complete all four visits or did not complete all 7 modules during a visit) will be handled using multiple imputation via chained equations (MICE; see for example Azur, Stuart, Frangakis, & Leaf, 2011). Missing outcome values will be imputed 48 times using linear regression and predictive mean matching. We will then apply the statistical model to each combination of observed and imputed data and will pool the resulting set of 48 model results using Rubin's rule. Subjects must have at least one post-baseline data point to be included in an analysis. Note because we are interested in the effect of abstinence, only data with biochemically-verified abstinence will be included – all data for the visit of and subsequent visits in which abstinence was no longer verified will be excluded for CB-Abst subjects. Covariates for imputing missing values will be:

- Non-missing outcome values at other time points;
- Outcome values at the baseline visit;
- The covariates listed above (age in years, biological sex at birth, baseline scores for CUDIT-R, and duration in years spent using cannabis).

Clinical Significance

In addition to determining whether there is a statistically significant difference between groups, we assessed clinical significance by computing standardized effect sizes for all contrasts of interest per each outcome. Effect sizes were estimated by dividing the estimate (transformed when necessary to be in the original scale of the measure) by the standard

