- Data were modeled using a normal distribution (i.e., the standard linear model).

1.2. The median of the response times for hits from the **RVP** module.

- The median over the set of response times for all correct responses (identification of target 3-digit sequences).
- Response time variable in milliseconds (ms), ranging from 100 to 1900 ms, with higher values indicating slower performance in detecting targets.
- Data were modeled using a normal distribution (i.e., the standard linear model).

Statistical model

We will use the same statistical models and approach for primary and secondary analyses as described for the primary outcomes. We will deem effects significant for $\alpha = 0.025$.

Power

Power was determined via an R script conducting a power analysis for a linear model with treatment and time effects, including a treatment by time interaction, and assuming subject-varying intercepts and slopes for change over time (Schoenfeld, 2009). The script can be found at the following link:

- <http://hedwig.mgh.harvard.edu/biostatistics/sites/default/files/public/powslopes.r>

We assumed each group would have an initial set of 70 subjects. Though we had a retention rate of 93% in our pilot trial with 100% of retained participants with complete data, power calculations assumed a conservative 4% drop-out per week (i.e., just under 85% retention at Week 4). Power was computed using outcomes from a prior study ([name] et al., 2018):

- The mean response latency (in ms) for correct responses from the Attention Switching Task (AST) module.
- The mean switching cost (in ms; equivalent to the multitasking cost in the MTT module) from the AST module.
- The mean response latency (in ms) to correct choice on a first attempt from the Delayed Match to Sample (DMS) module.

Though based on different modules from the CANTAB than those currently used, these outcomes were chosen because of (a) the availability of prior data, (b) compatibility with the assumptions of the power analysis software, and (c) because of their overlap with the domains of interest, as the AST (which is very similar to the MTT) examines executive functioning and the DMS examines memory.

Power analyses indicated we would have an 80% chance to detect a difference at 2-sided alpha of .05 if the true difference between CB-Abst and CB-Mon (assuming learning in both groups) over 4 weeks of abstinence was:

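### The SAP's 80% power belongs to a random-slope interaction test at alpha 0.05 on proxy latencies; it is not the power of the confirmatory constant-effect test, and no power is stated for any listed outcome

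*SAP*

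**What the plan says.** **Power calculation (SAP, Power).** The calculation is described as a "power analysis for a linear model with treatment and time effects, including a treatment by time interaction", "assuming subject-varying intercepts and slopes for change over time". It assumes 70 per group and 4% drop-out per week. The result is "Power analyses indicated we would have an 80% chance to detect a difference at 2-sided alpha of .05" if the true CB-Abst v CB-Mon difference is 11 ms/wk (AST mean latency), 12 ms/wk (AST switching cost) or 67 ms/wk (DMS mean latency). The section discloses that these modules are not the ones used in this study and gives reasons for choosing them.

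**Confirmatory test (SAP, Statistical model, Key confirmatory effect, Covariates).** The contrast is CB-Abst against CB-Mon, "testing whether a constant effect of abstinence exists, averaged over all time points". The model is a GEE assuming that "the observations for a subject per each study visit were uncorrelated". Time is "coded as week 1 = -3, week 2 = -1, week 3 = 1, and week 4 = 3", and the subject's "baseline value for a given outcome, converted to a z-score" is a covariate. The model is additive, "with main effects for a) the impact of abstinence and b) change over time, but no treatment by time interaction".

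**Alpha (SAP, Multiple comparisons).** Bonferroni within module: 0.05 for SST; 0.025 for PAL, SSP, OTS and SWM; 0.0167 for VRM; 0.0125 for MTT.

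**Secondary analysis 1 (SAP, Secondary analyses).** It adds group by linear time to the model above and tests it at the module alpha.

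**Outcomes (SAP, Selection of outcomes).** Seventeen are listed. VRM has four (items 1.5 to 1.8), one of them added after the first unblinded analyses.

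**Exclusions (SAP, Missing data).** CB-Abst data are dropped from the first visit at which abstinence is no longer verified.

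**The concern.** The term that was powered, treatment by time, is absent from the confirmatory model. The alpha in the calculation is the confirmatory alpha for one module of seven. The powered outcomes are latencies from two modules outside the battery. The DMS latency represents memory, but no primary memory outcome is a latency. The 4% weekly drop-out makes no stated allowance for CB-Abst visits excluded once abstinence is unverified.

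The stake is interpretation. A reader who meets a null primary result, particularly for memory, may take the 80% as evidence that a relevant effect would have been found. The SAP gives no basis for that.

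**Working it through.** **1. What can be checked in the Power section.** Retention: 0.96^4 = 0.849, which agrees with just under 85%. Ratios to the pilot: 11/21 = 52.4% and 67/160 = 41.9% agree with the text; 12/25 = 48% against a stated 50%, which rounding of 12 and 25 could explain. The 80% itself cannot be reproduced, because no intercept, slope or residual variance is given.

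**2. Alpha alone, same test and same slopes.** No variance assumption is needed. Effect/SE for 80% power at two-sided 0.05 is 1.960 + 0.842 = 2.802. Power at another alpha = Phi(2.802 - z), and the detectable slope scales by (z + 0.842)/2.802.

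| Alpha | z | Power at stated slopes | Ratio | Slopes for 80% (ms/wk) |
|---|---|---|---|---|
| 0.05 (SST) | 1.960 | 80% | 1.000 | 11, 12, 67 |
| 0.025 (PAL, SSP, OTS, SWM) | 2.241 | 71% | 1.100 | 12.1, 13.2, 73.7 |
| 0.0167 (VRM as stated) | 2.393 | 66% | 1.155 | 12.7, 13.9, 77.4 |
| 0.0125 (MTT) | 2.498 | 62% | 1.192 | 13.1, 14.3, 79.9 |

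Pilot-sized AST slopes (21 and 25 ms/wk) keep over 99% power in this test at 0.0125.

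**3. VRM.** The SAP divides 5% by the number of outcomes in the module. Four outcomes give 0.05/4 = 0.0125. The stated 0.0167 is 0.05/3.

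**4. Outcome types.** Binomial: PAL 2 + SSP 2 + VRM 4 + MTT 1 + OTS 1 + SWM 2 = 12, of which 8 are memory (8 of 8) and 4 executive (4 of 9). Normal: MTT 3 + OTS 1 + SST 1 = 5. AST and DMS supply none of the 17.

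**5. Power of the actual primary test (illustrative).** All variances here are assumptions: residual SD 1, intercept SD 1-3, random-slope SD 0-0.4 per week, intercept and slope uncorrelated; 70 per arm, 4% weekly drop-out. For each combination, d is the slope difference with 80% power at 0.05 in the random-slope model. The primary test is the GEE on observed weeks 1-4 (group, linear time, baseline) with sandwich variance, no imputation and no excluded CB-Abst visits. If the difference is d x week, the group coefficient estimates d times the average observed week:

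(0.96x1 + 0.9216x2 + 0.8847x3 + 0.8493x4)/(0.96 + 0.9216 + 0.8847 + 0.8493) = 8.855/3.616 = 2.45.

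Power = Phi(2.45d/SE - z). The SAP does not say which visits the power script used, so both readings are shown. With weeks 0-4, baseline group means are taken as free or common; with weeks 1-4, group levels are free.

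| Script's visits | Test | 0.05 | 0.025 | 0.0125 |
|---|---|---|---|---|
| Weeks 0-4 | Primary, difference grows linearly | 53-77% | 42-68% | 32-58% |
| Weeks 1-4 | Primary, difference grows linearly | 83-95% | 74-92% | 66-87% |
| Weeks 0-4 | Secondary analysis 1 | 40-63% | 30-52% | 22-42% |
| Weeks 1-4 | Secondary analysis 1 | 77-80% | 68-71% | 58-61% |

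If the week-4 difference (4d) is present from week 1, primary power on the weeks 0-4 reading is 91-99% at 0.05 and 79-97% at 0.0125; on the weeks 1-4 reading it is higher still.

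The grid's intraclass correlation runs from 1/(1+1) = 0.50 to 9/(9+1) = 0.90, wider than the test-retest range of 0.6-0.75 in the protocol's Power Analysis. A narrower grid (intercept share 0.60-0.75, slope variance 0-0.05 of intercept plus residual variance, weeks 0-4) gives 57-76% at 0.05 and 36-56% at 0.0125 for the linear case.

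**The case against.** The SAP openly states the interaction model, the random slopes, the alpha of 0.05 and the use of proxy modules, and it nowhere claims 80% for the primary test or for counts. That is correct and limits the fault to a missing link. The section still does not tell the reader that the test, the alpha and the outcome type all differ from the confirmatory analysis.

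Secondary analysis 1 also tests a slope difference, so a reader might infer that the 80% is simply wrong for it. That goes too far. The mismatch there is narrower: GEE on weeks 1-4 instead of random slopes, and, except for SST, a lower alpha. On the weeks 1-4 reading nearly all of the loss comes from alpha.

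A reader might also infer that the trial is underpowered. The documents do not support that. The sign of the gap depends on the visits in the script, the shape of the effect and the unreported variances. Nor does the count of 12 binomial outcomes mean that the other five have stated power; they have at most proxies.

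Finally, data collection ended in 12/2022, and the planned confidence intervals and standardised effect sizes already serve interpretation. This lowers the importance of the point but does not make the power statement fit the analysis.

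**Conclusion.** The point holds as a mismatch between power calculation and analysis, not as an arithmetic error in the 80%. From the text alone: the 80% is not the power of the confirmatory test; alpha alone takes the stated slopes to 71%, 66% or 62% in the random-slope test; VRM's threshold contradicts the SAP's own rule; none of the 17 primary outcomes has directly stated power; and a latency calculation is no guide to the 12 count outcomes.

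The size and direction for the primary test are unknown. The ranges in the second table rest on assumed variances and on an unstated visit schedule, and they fall on either side of 80%. The 80% should not be used to interpret a null primary result. Severity is minor.

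**What to change.** 1. In the Power section, state that 80% at 11, 12 and 67 ms/wk applies to a random-slope interaction test at alpha 0.05 on proxy latency outcomes, and is not the power of the confirmatory test.
2. Give power or the minimum detectable difference for the primary GEE test at each module's alpha, with VRM corrected to 0.0125. Use the pilot variance components, state the visits included, allow for the expected excluded CB-Abst visits, and show both a constant and a linearly growing difference.
3. For the 12 count outcomes, calculate power or state that none was calculated, and say that the DMS latency figure does not give power for the memory outcomes.

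The cost is a recalculation and a few sentences. Apart from the VRM threshold, no test, sample size or design decision changes. The stated power may become less favourable.
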